D6. Statistical Analysis Plan- Efficacy analyses will be performed for the intent-to-treat (ITT) population, our primary analysis, and for fully and partially compliant per-protocol (PP) populations. The ITT population will include all participants in the group to which they were randomized, regardless of any protocol deviation including non-compliance, adverse events, or loss of follow-up. The PP populations will include participants in the group according to the intervention actually received, but a separate analysis will be performed for those who were fully compliant (at least 80% of sessions completed) and for those who were partially compliant (at least one session completed). A complier-average causal effect (CACE) analysis using a latent class modeling approach will also be performed on both fully and partially compliant populations. Patients missing a baseline value of a continuous efficacy outcome measure will be excluded from all analyses and maximum likelihood estimation methods will be used to handle missing data arising from an unobserved follow-up visit¹²².

Aims 1a and 1b: The primary (overall cognition) and secondary (executive functions, episodic memory domains, and computer-based tests) cognitive outcome measures (all summaries of z-scores), will each be analyzed using a mixed model analysis of covariance (ANCOVA) with time of assessment (baseline or 12 weeks) as the within-subjects factor, treatment group (HBOT vs. sham) as the between-subjects factor and baseline value of the outcome measure as the covariate. *Both, subject and 'cluster' (the variable used to identify to which group of at least 3 subjects each individual is assigned) will be modeled as random effects to account for the correlation among repeated measurements made over time within a subject as well as potential 'cluster effects' arising from blocks of at least 3 patients receiving treatment at a particular time after randomization.* An interaction term between time of assessment and treatment group will be included in each model allowing for estimation of the mean change from baseline to 12 weeks in each treatment group as well as a test for difference

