in change scores between groups. A test of parallel treatment effects across the range of baseline values will be conducted by including a three-way interaction term among time of assessment, treatment group and baseline value of the outcome variable as well as all lower order two-way interaction terms. If the three-way interaction term is statistically significant it will be retained in the final model and estimates of the difference in mean change scores between treatment groups will be evaluated at selected percentiles of the baseline distribution. Secondary mixed model ANCOVA analyses will be performed for cognitive assessments at 6 and 12 months following treatment. As an exploratory analysis, linear mixed effects models will assess the relationship between treatment group (fixed effect) and the longitudinal trend (random intercept and slope for each subject) in the primary and secondary cognitive outcome measures, assessed at 12-weeks, 6 months and 12 months following treatment. The primary hypothesis will be tested by assessing the interaction between treatment group and time of cognitive follow-up assessment, with a significant interaction indicating a difference in longitudinal cognitive trends between treatment groups. Potential confounders (age, gender, education, *duration of T2D, HbA1c, diabetes medications [insulin vs. no medications and oral agents vs. no medication], levels of atrophy and white matter hyperintensities*) will be included as covariates if there is imbalance at baseline ($p<0.1$) or association between the covariate and the response ($p<0.15$).

To explore whether specific dichotomized T2D characteristics (such as the last HbA1c level (dichotomized at 7) in the Diabetes Registry, the number of T2D complications, and the number of severe hypoglycemic episodes in the year preceding randomization) are associated with greater improvements following treatment with HBOT, mixed effects ANCOVA models similar to those for Aims 1 and 2 will add a main effect for the specific T2D characteristic and an interaction term between treatment group and the characteristic. Using the MHS dataset, we will also explore associations of dosage of the most prevalently used medications with cognitive outcomes. When potential confounders are associated with cognitive outcomes, this also may identify subgroups for which HBOT is particularly effective.

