Aims 2a and 2b: CBF and cerebral glucose utilization will be analyzed with a similar strategy to Aims 1a and 1b except that there will be no 6 month assessment. Mixed effects ANCOVA models will be used to compare changes in these outcome measures from baseline to 12 weeks following treatment, and, as exploratory analyses, linear mixed effects models will be used to assess relationships between treatment group (fixed effect) and the longitudinal trend (random intercept and slope for each subject) in MRI-ASL and FDG-PET outcome measures, assessed at 12-weeks and 12 months following treatment. Vascular effects of HBOT vs. Sham: Since CBF derived from ASL perfusion may represent combined effects of neural metabolism and vascular effects, a secondary mixed effects ANCOVA model (similar to Aim 2b) of vascular changes from baseline to 12 weeks as measured by ASL CBF will adjust for neural metabolism derived from FDG-PET.

Aim 3: Outcome measures (changes in CBF and cerebral glucose utilization) identified as having significant associations with treatment group in Aims 2a and 2b will be further explored as mediators of the relationship between treatment group and the change in cognition. To ensure that measurement of mediator

variables precedes measurement of cognition, we will define the outcome as the change in cognition from baseline to 12 months, and the mediators as changes in CBF and cerebral glucose utilization, from baseline to 12 weeks. The product of coefficients approach will be used within a multiple mediator modeling framework to provide point estimates of both the specific indirect effect (i.e. the effect of treatment group on the change in cognition from baseline to 12 months via a mediator among other mediators in the model) and the total indirect effect (i.e. the sum of specific indirect effects for all mediators in the model). The bootstrapping method⁹³ will be used in each multiple mediator model to compute bias-corrected standard errors (and 95% confidence intervals) for the specific and total indirect effect point estimates.

D7. Power Analysis and sample size justification

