Aim 1. Power is presented for detecting the difference in mean change (from baseline to 12 weeks) in overall cognition z-scores between the sham and HBOT treatment groups. Power calculations are based on two-sample t-tests and are conducted with a 2-sided 5% significance level (**Table 3**). A 2-sample t-test provides a more conservative power estimate than the proposed mixed model approach, which is expected to explain more variability and thus have more power to detect the same effect size with the same sample size.

The predicted mean change in the sham group from baseline to 12 weeks is -0.02 (based on the IDCD 12-week change in overall cognition). Assuming an SD of 0.50 in both the sham and HBOT groups, with a minimum sample size of 67 patients per arm, we have 80% power to detect an improvement in the HBOT group of 0.224, a “medium” effect size of 0.49. To account for an anticipated dropout rate of 13% (a reasonable estimate compared to the 5% dropout rate in our stroke study), we plan to enroll 77 patients per group for a total of 154 patients. Our HBOT trial years after mild traumatic brain injury⁷⁴ had an effect size of 0.47 for information speed processing which is clinically comparable to our primary outcome measure of overall cognition, and our HBOT trial on stroke patients⁷⁸ showed an effect size of 0.49 for the National Institutes of Health stroke scale, suggesting our detectable effect size of 0.49 is feasible.

Aim 2: As for Aim 1, power is presented for detecting the difference in the mean changes in CBF velocity and cerebral glucose utilization between the Sham and HBOT groups. Assuming a mean change in CBF velocity of -0.45 in the Sham group and an SD of 5.6 in both groups, with a minimum sample size of 67 patients per arm we have 80% power to detect an improvement in the HBOT group of 2.28, an effect size of 0.49. *To account for an anticipated dropout rate of 13%, we plan to enroll 77 patients per group for a total of 154 patients.* For cerebral glucose utilization, assuming a mean change in the sham group of -0.08 and an SD of 4.40 in both groups, with

Table 3: Two group t-test of equal means, equal n's)*			
	Outcome		
	Overall Cognition z-score	CBFV [†]	CGU [‡]
Sham Mean Change, D ₁	-0.020	-0.450	-0.08
HBOT Mean Change, D ₂	0.224	2.28	2.065
Difference in means, D ₁ -D ₂	-0.244	-2.73	-2.145
HBOT SD	0.50	5.60	4.40
Minimum N per group	67	67	67
Enrollment N per group**	77	77	77

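### The primary model uses baseline both as a response row and as the covariate, so the treatment-by-time standard error is too small and baseline adjustment gains nothing

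*Combined protocol and SAP*

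**What the plan says.** Section D6, Aims 1a and 1b, sets out one model for the primary composite and for each secondary cognitive outcome:

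- Factors and covariate: "time of assessment (baseline or 12 weeks) as the within-subjects factor, treatment group (HBOT vs. sham) as the between-subjects factor and baseline value", the last entering as covariate. The time factor has two levels, and baseline is one of them.
- Covariance: subject and cluster "will be modeled as random effects to account for the correlation among repeated measurements made over time within a subject", and to absorb cluster effects.
- Test: "An interaction term between time of assessment and treatment group will be included in each model", which gives "estimation of the mean change from baseline to 12 weeks in each treatment group as well as a test for difference" between the groups in those changes.
- Parallelism check: a three-way term (time, group, baseline) is added together with its two-way terms. "If the three-way interaction term is statistically significant it will be retained in the final model".
- Missing data: "maximum likelihood estimation methods will be used to handle missing data arising from an unobserved follow-up visit", so a patient with only a baseline score still contributes a row.

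For Aims 2a and 2b, D6 says "CBF and cerebral glucose utilization will be analyzed with a similar strategy to Aims 1a and 1b". Section D7 sizes the trial with a t-test on change scores and adds: "A 2-sample t-test provides a more conservative power estimate than the proposed mixed model approach, which is expected to explain more variability".

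**The concern.** An ANCOVA conditions on baseline and models what comes afterwards. A repeated-measures model of change has baseline among the responses and no baseline covariate. The plan combines the two, so one of each patient's two responses is regressed on itself. That row has an artificially small residual, and the residuals of the two rows are negatively correlated. A random intercept cannot represent a negative correlation.

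This is the test of the primary outcome. The same form serves the secondary cognitive outcomes and the two imaging outcomes, and D6 (Aim 3) then picks mediators by their significance in the imaging models. If the standard error is too small, the p-values and confidence intervals are anti-conservative throughout. If the covariate does nothing for the tested contrast, the extra precision that D7 expects will not appear.

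**Working it through.** **Inputs.** From D7: difference in mean change 0.224 − (−0.020) = 0.244; SD 0.50, read as the SD of change; 67 evaluable and 77 enrolled per arm; 13% dropout; two-sided 5%. Assumed, because the documents do not give it: the baseline to 12-week correlation ρ, taken from 0.5 to 0.9, with equal variances at the two visits.

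**The plan's own figure.** Noncentral-t power for 0.244 with SD 0.50 is 79.5% at 66 per arm and 80.1% at 67, so 67 reproduces. 67/(1 − 0.13) = 77.01, which is 77 to rounding. The sample size is not in question.

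**Step 1: the estimate.** The covariate takes the same value on both of a patient's rows, so it cancels from the within-patient difference. With complete data the interaction equals the difference in raw mean change. Simulated fits agreed to five decimals in every replicate. Its true standard error is 0.50 × √(2/67) = 0.0864.

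**Step 2: the model's standard error.** Let s² be the variance at each visit, so the 12-week score has slope ρ on baseline and residual variance s²(1 − ρ²). On the baseline row the slope is 1.

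- Implied subject variance: −(1 − ρ)²s²/4, which is never positive. The estimate goes to zero. In bounded REML fits this happened in 88% to 100% of runs, depending on ρ and the numerical cut-off.
- With subject variance zero, the fitted common slope is (1 + ρ)/2.
- Residual variance on the baseline row: (1 − ρ)²s²/4. On the 12-week row: (1 − ρ²)s² + (1 − ρ)²s²/4.
- The model's variance for a within-patient difference is the sum of these two: s²(1 − ρ)(3 + ρ)/2.
- The true variance of the difference is 2s²(1 − ρ).
- Ratio: (3 + ρ)/4. True size: 2[1 − Φ(1.96 √((3 + ρ)/4))].

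**Step 3: the usual ANCOVA.** With the 12-week score as the only response, the variance is s²(1 − ρ²), which is (1 + ρ)/2 of the change-score variance.

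| ρ (assumed) | SE ratio, written model | True size, formula | True size, simulated | ANCOVA SE | ANCOVA power at 0.244 |
|---|---|---|---|---|---|
| 0.5 | 0.935 | 6.7% | 6.5–6.9% | 0.0748 | 90% |
| 0.7 | 0.962 | 5.9% | 6.0–6.4% | 0.0796 | 87% |
| 0.8 | 0.975 | 5.6% | 5.6–5.9% | 0.0820 | 85% |
| 0.9 | 0.987 | 5.3% | 5.3–5.7% | 0.0842 | 83% |

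Power is by normal approximation; simulation gave 90%, 85–86%, 84% and 82%. ANCOVA rejected 4.5–5.3% of the time under the null. The change-score contrast has about 80% power. The written model appears to have 81–84%, but the excess comes from its understated standard error.

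**Step 4: the trial as planned, with dropout.** Patients with only a baseline row add artificially small residuals, and the model counts them as information. With 77 baseline rows and 67 follow-up rows per arm:

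- Common slope b = (77 + 67ρ)/144.
- Pooled residual variance: [77(1 − b)²s² + 67{(1 − ρ²)s² + (ρ − b)²s²}]/144, multiplied by 2(1/77 + 1/67) for the interaction.
- At ρ = 0.5, s² = 0.25 and b = 0.767. The model SE is 0.0758 and the true SE 0.0854, a ratio of 0.887 and a size of 8.2%. Simulation gave 8.5–8.8%.
- At ρ = 0.7, 0.8 and 0.9 the formula gives 7.6%, 7.3% and 7.0%. Simulation gave 7.6%, 6.9% and 6.8–6.9%.
- As ρ approaches 1 the variance ratio tends to 67/77 = 0.870, a size of 6.8%. With dropout the error therefore does not vanish at high correlation.

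The simulations used 10,000 to 20,000 trials per setting, random dropout where applicable and no true cluster effect. Most set the subject and cluster variances at zero, in line with the boundary result.

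**The case against.** Five points deserve an answer.

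1. *The parallelism check brings in baseline-by-time.* If that term stays, the interaction at mean baseline becomes the ANCOVA estimate, and the efficiency complaint disappears. D6 states retention only for a significant three-way term and does not say that baseline-by-time otherwise remains. The natural default lacks it, though the text could be clearer.
2. *The standard error depends on implementation.* An unstructured residual covariance, or a variance component allowed to go negative, would give the correct change-score standard error. That is true, but D6 specifies a random subject effect. Even the correct change-score standard error brings no gain with complete data.
3. *ρ is assumed, and 0.5 is probably low.* If the composite averages eight unit-variance z-scores, a change SD of 0.50 with ρ = 0.5 implies a mean inter-test correlation of only 0.14. Inter-test correlations of 0.3 to 0.5 imply ρ of about 0.68 to 0.78, and then the size is about 6.0% to 5.7% with complete data. This stands: the middle of the table is the likelier place. With dropout the same range gives 7.6% to 7.3%.
4. *CBF is barely affected.* D2j reports test-retest reliability above 0.95. At ρ = 0.95 the complete-data size is about 5.1% and the ANCOVA saving 2.5%. That is fair for complete scans; the dropout effect remains.
5. *Planned power is not lost.* Correct. D7 sized the trial on the change score. What fails is the expectation of more.

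**Conclusion.** The concern holds for the model as D6 writes it. The test of the primary outcome is anti-conservative: about 5.3% to 6.7% instead of 5% with complete data, and about 7% to 8% or a little more with the planned dropout. The first range assumes ρ from 0.9 down to 0.5, equal variances and a subject variance bounded at zero; the second also assumes that dropout is random. The baseline covariate contributes nothing to the tested contrast when data are complete, so the 5–25% variance reduction available from ANCOVA (1 − (1 + ρ)/2) is forgone, along with roughly 2 to 10 points of power. The size error is modest, but it is systematic, it favours a positive finding, and it is carried to every outcome analysed the same way. It should be corrected before analysis. The sample size of 67 evaluable and 77 enrolled per arm is unaffected.

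**What to change.** Rewrite the model in D6 in one of two ways:

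- **Baseline as covariate only.** Take the 12-week score as the response, with group, baseline and the cluster effect. If the later visits are to share the model, use the 12-week, 6-month and 12-month scores with group, visit, group-by-visit, baseline and baseline-by-visit, and an unstructured within-patient covariance. The primary estimate is the HBOT minus sham contrast at 12 weeks.
- **Baseline as response only.** Keep both visits as responses, constrain the group means to be equal at baseline, drop the baseline covariate and use an unstructured covariance.

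Either way, restate the parallelism check as a group-by-baseline term (by visit, if several visits are modelled) in the chosen form, and use the same form for CBF and glucose utilization in Aims 2a and 2b. The shared model for the later visits is optional; removing the double use of baseline is the essential part. D7's statement about explained variability then becomes reasonable. The cost is SAP wording only: same data, no extra visits and no extra patients.

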D2c. Procedures- **Table 2** presents study procedures for each subject. HBOT sessions will take place in Asaf Harofeh Medical Center; informed consent and all other assessments, including cognitive, functional, MRI, and FDG-PET will be performed at the Sheba Medical Center. Adverse event monitoring is done at every HBOT and sham session, by a nurse in the chamber throughout the session and a physician always present. Physical exams and blood collection for safety monitoring will occur before randomization, and at 12 weeks. Medication review will occur before randomization, before and after the intervention, and 6 and 12 months later, with cognitive testing at these times except before randomization. The T2D-related biomarkers (Blood test, MRI ASL and FDG-PET) will be assessed before and after the intervention, and 12 months later. After intervention, a questionnaire will examine whether blindness was maintained. At the end of the participant's 12 months' participation in the trial, the participant can choose to receive HBOT treatment for which the costs will be covered by the study team. At the end of the second HBOT treatment course, an additional neuropsychological assessment will be administered to the participants.

D2d. Randomization and Blinding of Intervention-Eligible candidates will be randomized with equal probability to the HBOT and sham interventions. When a cluster of at least 3 subjects from one of the interventions is filled, the intervention for that cluster will begin (77 subjects will be recruited for each treatment). Clusters will be a random effect in the analyses (see D6). Three study technicians who activate HBOT or sham protocol sessions will be the only unblinded staff who have the key for the subjects' group assignments. All subjects and other clinic staff will remain blinded to group assignment. Study nurses will monitor AEs during all sessions and a physician will be present during each session. Importantly, staff from Sheba, who assesses outcomes, will not be exposed to the subjects during their intervention and vice-versa.

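### As D6 most naturally reads, the cluster random effect cancels from the time-by-treatment test, so the primary analysis does not account for the post-randomization cluster effects it names

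*Combined protocol and SAP*

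**What the plan says.** D2d randomizes individuals 1:1. Treatment starts once at least three subjects of the same arm are available, so every cluster lies wholly within one arm. D2d adds that cluster will be a random effect in the analyses and refers to D6.

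For the primary and secondary cognitive outcomes (Aims 1a and 1b), D6 describes a mixed-model ANCOVA "with time of assessment (baseline or 12 weeks) as the within-subjects factor". Treatment is the between-subjects factor and the baseline value is the covariate. Subject and cluster are the only random effects named. The cluster term is there for "potential 'cluster effects' arising from blocks of at least 3 patients receiving treatment at a particular time after randomization". The treatment effect is the time-by-treatment interaction, that is, the difference in mean change.

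D6 does mention a slope, but only in the exploratory model of the "longitudinal trend (random intercept and slope for each subject) in the primary and secondary cognitive outcome measures", and only for subject. The imaging outcomes are to be analysed in a similar way.

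For sample size, D7 states: "Power calculations are based on two-sample t-tests". It gives no ICC, maximum cluster size or design effect.

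**The concern.** Patients who share chamber sessions do so after baseline. Any effect of being treated together therefore acts on the change from baseline to 12 weeks. A random effect that shifts a cluster's baseline and 12-week scores equally cannot represent this, because it disappears when one is subtracted from the other.

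Since clusters are nested in arm, between-cluster variation in change goes straight into the treatment contrast. If the standard error omits it, the primary test rejects too often and its confidence interval is too narrow, while the report would state that clustering had been accounted for. Secondary and imaging outcomes would inherit the problem.

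**Working it through.** **The plan's own figure.** D7 gives a sham change of −0.02, an HBOT change of 0.224, an SD of change of 0.50, and a test "conducted with a 2-sided 5% significance level".
- Difference: 0.224 − (−0.02) = 0.244. Effect size: 0.244/0.50 = 0.49.
- The noncentral t gives 67 per arm, with power 80.06%. This reproduces D7.
- Dropout: 67/0.87 = 77.01, in line with the 77 enrolled per arm.

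**Why the term cancels.** Write s for the subject effect, c for the cluster effect, b for the baseline covariate and g for arm:
- baseline row: y0 = β0 + βg·g + γb + s + c + e0
- 12-week row: y1 = β0 + βt + (βg + βgt)·g + γb + s + c + e1
- difference: y1 − y0 = βt + βgt·g + (e1 − e0)

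The terms s, c and γb all drop out. The standard error (SE) of βgt depends only on the residual variance.

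**Numerical check.** Generalized least squares SE of the interaction, with 66 per arm (divisible by 3, 6 and 11) and SD of change 0.50:
- Complete data: 0.08704 for a cluster variance of 0, 0.05, 0.10 or 0.50, at cluster sizes 3, 6 and 11. This equals 0.50 × √(2/66), the SE with no cluster term.
- 13% of 12-week rows missing: from 0.09244 to at most 0.09271, a shift of 0.3%.
- Cluster effect placed on the change, ICC 0.05, complete data: 0.0913 for clusters of 3 and 0.0973 for clusters of 6.

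**Size of the error.** If change has ICC ρ within clusters of size m, the true variance of the contrast is larger by the design effect DE = 1 + (m − 1)ρ. A test that leaves this out has two-sided type I error 2[1 − Φ(1.96/√DE)]. For example, m = 3 and ρ = 0.05 give DE = 1.10, 1.96/√1.10 = 1.869, and an error of 6.2%. The last column is the power of a correctly specified analysis with D7's inputs and 67 per arm, before any loss of degrees of freedom. All ICCs are assumptions.

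| Cluster size | ICC | DE | Type I error | Power |
|---|---|---|---|---|
| 3 | 0.01 | 1.02 | 5.2% | 79.3% |
| 3 | 0.02 | 1.04 | 5.5% | 78.5% |
| 3 | 0.05 | 1.10 | 6.2% | 76.2% |
| 3 | 0.10 | 1.20 | 7.4% | 72.6% |
| 5 | 0.01 | 1.04 | 5.5% | 78.5% |
| 5 | 0.02 | 1.08 | 5.9% | 77.0% |
| 5 | 0.05 | 1.20 | 7.4% | 72.6% |
| 5 | 0.10 | 1.40 | 9.8% | 65.9% |

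**Plausible cluster sizes.** D4 gives about 47 subjects a year, or 23.5 per arm. Filling a cluster takes 52 × 3/23.5 = 6.6 weeks for 3 subjects, 11.1 weeks for 5 and 24.3 weeks for 11. The note to Table 2 has treatment starting within three weeks of the baseline assessments.

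**Simulation.** In 2,000 simulated trials per setting with no treatment effect, clusters of 3 and ICC 0.05, a change-score t-test with no cluster term rejected in 6.9%. A test on cluster-level change rejected in 5.1%. Monte Carlo error is about 0.5 to 1 point.

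**The case against.** The strongest reply is that D6 never calls the cluster effect an intercept. A cluster-by-time term is also a random effect, and it would serve the purpose D6 states. The phrase about intercept and slope belongs to a different, exploratory model. This stands in part: what is printed is an incomplete covariance structure. But D6 lists subject and cluster side by side with no time interaction, and code written from that text would give the version that cancels.

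Second, the effect may be small. Randomization is individual, subjects read or watch TV during sessions, and the Sheba assessors do not meet subjects during treatment. This also stands. With clusters of 3 and an ICC of 0.01, the error rate is 5.2%.

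Third, a reader might take the chamber's 11 seats as the cluster size and infer type I error of 11% or more (11.0% by formula at ICC 0.05). The documents do not support that: 11 is a capacity, and a cluster that large would need about 24 weeks to fill.

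Fourth, simulating the whole D6 model gives higher rates, for example 7.7% for clusters of 3 at ICC 0.05. Those rates mix in a separate defect, the use of baseline as both response row and covariate, and should not be charged to clustering.

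Finally, dropping the baseline row as a response cures both problems at once. That is correct, and it is a reason to prefer that repair.

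**Conclusion.** The point holds on the plain reading of D6: the cluster effect has no bearing on the tested contrast with complete data and almost none with 13% dropout. The primary standard error would then be too small whenever treatment clusters differ in change. A reader might infer that the trial has a seriously inflated error rate, or that the plan states an intercept-only cluster effect. Neither is established. The ICC and cluster size are not given, and the intercept is an inference from the text. Over the assumed ICCs of 0.01 to 0.10, the error rate is 5.2% to 7.4% for clusters of 3 and 5.5% to 9.8% for clusters of 5.

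This should be fixed, because it affects the primary p-value and interval and the repair is cheap. The absence of cluster from the exploratory trend models and the mediation bootstrap is secondary. Neither is the primary test, and D2d's general statement arguably covers them.

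**What to change.** In D6, put the cluster effect on the quantity that is tested. The preferred form models the 12-week score with baseline as covariate, treatment as fixed effect and a random intercept for treatment cluster, nested in arm, with Kenward-Roger or Satterthwaite degrees of freedom. This also removes the double use of baseline. If both rows are kept, add a random cluster-by-time effect and say so explicitly. Use the same structure for the secondary and imaging outcomes, and settle it before any unblinded analysis.

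The cost is a few lines of SAP text and code. If clustering is real, the interval widens and power falls below the D7 figure: about 76% rather than 80% at ICC 0.05 with clusters of 3. Degrees of freedom also fall. With 25 full clusters of 3 per arm, about 50 − 2 = 48 remain. D7 should state the ICC and cluster size it assumes.

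### The plan does not say which contrast decides the primary hypothesis if the treatment-by-baseline pretest is significant, so type I error runs from 0.05 to about 0.09 depending on the reading

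*Combined protocol and SAP*

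**What the plan says.** D6 (Aims 1a and 1b) analyses the primary composite with a mixed-model ANCOVA. Its time-by-treatment term gives the between-group difference in change from baseline to 12 weeks. D6 then checks whether the treatment effect is parallel across baseline values by adding a three-way term in time, treatment and baseline, with all lower-order terms. The rule is: "If the three-way interaction term is statistically significant it will be retained in the final model". In that event the differences in mean change "will be evaluated at selected percentiles of the baseline distribution".

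D6 does not give:
- the significance level of this pretest;
- which percentiles will be used, or how many;
- any multiplicity adjustment;
- the contrast that decides the primary hypothesis once the term is retained.

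It also does not say that the overall difference is dropped, or that a significant result at one percentile would count as success.

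D7 (Aim 1 and Table 3) powers the trial for a single overall difference in mean change: "Power calculations are based on two-sample t-tests and are conducted with a 2-sided 5% significance level".

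**The concern.** A data-dependent step decides whether the final model for the primary outcome yields one number or several. If it yields several, the plan leaves the analyst to choose the percentiles and to decide what counts as a positive trial. A reader of the results could not then establish that the primary test had a 5% error rate.

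There is a second route to the same problem. In a model that keeps the interaction, the time-by-treatment coefficient is the treatment effect at a baseline score of zero unless baseline is centred. D6 does not mention centring, and D2h does not say what the z-scores are standardised to. If zero is far from the trial's mean baseline, that coefficient is not the average effect.

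The ambiguity recurs. D6 applies the same model to the secondary cognitive outcomes and a similar strategy to the imaging outcomes. The paragraph on exploratory longitudinal trends adds to the doubt, because it describes its own group-by-follow-up-time interaction as the test of the primary hypothesis.

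**Working it through.** **Inputs from D7 (Aim 1, Table 3).** "The predicted mean change in the sham group from baseline to 12 weeks is -0.02"; "we have 80% power to detect an improvement in the HBOT group of 0.224"; "Assuming an SD of 0.50 in both the sham and HBOT groups, with a minimum sample size of 67 patients per arm"; 13% dropout; "we plan to enroll 77 patients per group for a total of 154 patients". Allocation is 1:1 (D2d).

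**Assumed, because D6 does not give them.** Pretest at two-sided 0.05; the percentile sets shown below; normal data; no cluster effect.

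**Step 1: the plan's own figure.** Difference = 0.224 − (−0.020) = 0.244; standardised, 0.244 / 0.50 = 0.488 (stated as 0.49). The normal formula gives n = 2 × (1.95996 + 0.84162)² × 0.50² / 0.244² = 2 × 7.849 × 0.25 / 0.059536 = 65.9, so 66 per arm. The exact noncentral t gives power of 79.5% at 66 and 80.06% at 67, so the stated 67 is the exact t-test answer. Dropout: 67 / (1 − 0.13) = 77.01, stated as 77. The figure reproduces, and it is for one overall difference.

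**Step 2: the two branches.** Let y be the change to 12 weeks, g the treatment indicator and x the baseline score.
- Model A: y = a + b·g + c·x + error. The test is on b.
- Model B: y = a + b·g + c·x + d·g·x + error. The effect at baseline value q is b + d·q, with variance Var(b) + 2q·Cov(b, d) + q²·Var(d).

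The rule tests d. If d is not significant, Model A is used; if it is, Model B is used. In Model B, b is the effect at mean baseline when x is centred, and the effect at score zero when it is not.

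**Step 3: type I error.** 100,000 simulated trials with no treatment effect at any baseline value, 67 per arm. Monte Carlo standard error is about 0.001. Both models contain baseline, so the test statistics do not depend on the slope or SDs chosen for the simulation.

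| Test used when the term is retained | Type I error |
|---|---|
| Effect at mean baseline | 0.050 |
| Effect at the median only | 0.050 |
| Any of 25th, 50th, 75th, unadjusted | 0.070 |
| Any of 10th, 50th, 90th, unadjusted | 0.086 |
| Any of 10th, 25th, 50th, 75th, 90th, unadjusted | 0.086 |
| Either of 5th, 95th, unadjusted | 0.091 |
| Five percentiles with Bonferroni | 0.061 |
| Coefficient at score zero, sample mean 0 SD away | 0.050 |
| Same, 0.5 SD away | 0.055 |
| Same, 1.0 SD away | 0.064 |
| Same, 1.5 SD away | 0.071 |

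The five-percentile result is also 0.086 at 77 per arm.

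**Step 4: where the excess comes from.** The pretest is falsely significant in 0.0503 of null trials, and in 77.3% of those at least one of the five percentiles is nominally significant: 0.0503 × 0.773 = 0.0389. The other branch contributes 0.0864 − 0.0389 = 0.0475, which matches 0.95 × 0.05. The total is 0.0864. If every retained trial counted as a success, the rate would be 0.0475 + 0.0503 = 0.0978 (in theory 1 − 0.95² = 0.0975), so that is the ceiling for a pretest at 0.05. Bonferroni within the retained branch does not restore 5%, because that branch is entered only when the interaction estimate is already extreme.

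**Step 5: with one contrast fixed.** If the Model A contrast is always the test, type I error is 0.050. Simulated power at 67 per arm is 80.0% for a difference of 0.244 with residual SD 0.50.

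**The case against.** The strongest reply is that the branch is written into the plan in advance and is a conventional check for parallel slopes. D6 speaks of estimates at percentiles, not of tests. The time-by-treatment contrast is defined first, D7 powers exactly that contrast, and nothing says it is withdrawn when the three-way term is retained. Under the null the branch is reached in only about 5% of trials, and the study describes itself as a pilot.

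Much of this stands, and it rules out three stronger readings that a reader might infer:
- **That the pretest inflates type I error as such.** It does not. The rate is 0.050 if the mean-baseline or the median effect remains the test.
- **That the percentile estimates replace the overall difference.** The text is silent on this, and silence is not replacement.
- **That the estimand is changed after the fact.** The condition that triggers the branch is pre-specified.

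The point about the coefficient at zero is also conditional. If the z-scores are standardised to the trial's own baseline, zero is the sample mean and the problem disappears. D2h cites norms for elderly people with type 2 diabetes but does not say that the z-scores are built on them.

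Two limits remain. The simulation uses the change-score form of the model without the cluster random effect that D6 plans. And if a real interaction exists, percentile-specific findings are not all false positives.

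The reply does not supply the missing rule. The trigger is pre-specified, but what follows from it is not.

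**Conclusion.** The point holds as a gap in the decision rule. A significance pretest settles the form of the final model for the primary outcome, and the plan names no contrast that stays primary when the term is retained. The documents do not establish that the error rate is inflated; they leave it undetermined, between 0.05 and about 0.09 over the readings examined. The upper figures require that any unadjusted percentile result may count as success, or that an uncentred coefficient is read well away from the sample mean. The documents state neither. The range rests on the assumptions listed in the working. The gap is worth closing before analysis because doing so costs almost nothing.

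**What to change.** Add to D6 that the primary test is always the overall between-group difference in change from baseline to 12 weeks, the contrast powered in D7, taken from the model without the treatment-by-baseline interaction, whatever the three-way test shows. Taking it at the mean-centred baseline in the model with the interaction also holds 0.050; the plan should commit to one of the two.

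Make the three-way interaction a secondary description, state its significance level, and name in advance the percentiles at which effects will be shown. The 25th, 50th and 75th would serve, but the choice is the sponsor's. Say that no percentile-specific result decides the primary hypothesis. In the exploratory trend paragraph, stop calling that interaction the test of the primary hypothesis.

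The cost is a sentence or two in the SAP. The sample size stays at 67 evaluable and 77 enrolled per arm, and the percentile estimates are still reported.
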